2.1.2. Classification of Cancer Status

Study masses will be classified as biopsy-confirmed cancer, biopsy-confirmed benign or Truth Panel benign from the PIONEER Study. Biopsy-confirmed high-risk masses will be included and will be classified as benign for purposes of effectiveness calculations.

2.1.3. Analysis Populations

Safety results for the safety population will be reported for the final masses read as was done for the PIONEER Pivotal Study.

Masses will be selected according to the Mass Sampling Plan. BBRF stratified by diagnosis, original site CDU BI-RADS, and whether the mammogram images were available in selecting the masses at random from the universe of qualified masses analyzed in the PIONEER Pivotal Study. The Sampling Plan depends solely upon clinical study and statistical criteria, including input from the FDA. SenoGram performance was not considered and had no impact on the plan, nor was the SenoGram development group involved. The masses to be sampled excluded masses used in the READER-01 study as well as masses used for training and testing readers. The sampling strategy reflected the overall benign mass (including high risk masses) and malignant mass distribution in the PIONEER Pivotal Study. When subjects had multiple masses, only the first mass was considered. Blocks of 120 masses were constructed to include 75 benign masses (including 3 high risk masses) plus 45 cancer masses according to the stratification noted above.

At the interim timepoint and after study completion, all protocol deviations (PD) will be reviewed. Technical protocol deviations (such as a system error which would not allow the SenoGram to be viewed or a technical issue that will not allow an image to be viewed by a reader) will be handled during a Protocol Deviation Meeting prior to the interim and final analysis; if an image display issue occurs, then that case will be re-presented to a reader once the technical issue is corrected. If the SenoGram would not display to a reader, that case would be excluded from the analysis. Finally, readers not completing all reads (i.e. due to illness or family emergency) for non-study related reasons will be replaced by one of the pre-determined five back-up readers as necessary. Seno will not have access to any data from readers that did not complete all reads. No reader will be excluded as an outlier.

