0.1 :	15 :	854 :	0.801

Initially, 360 masses will be read by all readers for the purposes of performing the interim analysis to assess the sources of variation and to rerun the sample size estimate for the primary effectiveness endpoint. Neither futility nor efficacy will be assessed; this is not an adaptive design.

The sample size may be increased from the minimum of 480 image sets to a maximum of 840 image sets (7 complete blocks) in increments of 120 masses per block. All original color balance masses will be replaced with comparable masses and image sets within the final analysis from the PIONEER Pivotal overage masses.

The maximum sample size to be used for the study will be capped at 840 masses. An overage mass set will be set aside in case quality control issues are found with the images and replacement masses are needed. After excluding the pool of 840 masses and overage masses, approximately 900 masses will remain for independent SenoGram training. No masses used to train the SenoGram, will be in the pool of 840 study masses plus overage. We have removed the 29 masses from the pool of study masses which were mistakenly included from the original color balance algorithm.

Every effort will be made to identify missing reader generated data in real time. Each block of 120 masses will include 75 benign (72 benign + 3 high risk) and 45 malignant masses to represent the PIONEER study.

With the exception of masses excluded due to protocol deviations, all complete reads will be included in all analyses, consistent with an "Intention-to-Diagnose" approach.

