 13. For 80% power, a two-sided hypothesis test with a two-sided 5% alpha and 15 readers, a sample size of 854 image sets is needed; the 79% power with 840 image sets is deemed adequate to test the primary hypothesis test; the sample size was calculated using the same intra- and inter-reader standard deviation observed in the READER-01 Feasibility Study.
 14. A blinded interim analysis is planned after all readers complete the reading of the first three blocks (360 -10 Color Balance = 350 image sets). The interim analysis will only assess the reader variability associated with the primary endpoint; the sample size may be left at 480 image sets or increased up to 840 image sets based solely on the variability determined from the primary analysis.
 15. READER-01 Feasibility Study data will not be combined with the READER-02 Pivotal Study data but may be referenced in the final Pre-market Approval (PMA).
 16. Effectiveness analyses (interim and final) will be performed without the CB cases as the primary analysis. The interim analysis will be based on 350 masses without replacement while the final analysis will be based on the sample size to be determined to potentially include all or some of the 29 replacement cases.
 17. For completeness, a pre-defined subset of the PIONEER Study tables and listings will be regenerated for the subset of 480 to 840 masses using the READER-02 Pivotal Study data.
 18. For completeness, the differences which can be detected with 80% power will be calculated for the primary endpoint (specificity gain at 98% sensitivity) and for the secondary endpoint (pAUC over 95-100% sensitivity).
 19. A hierarchical testing strategy will be implemented to extend labeling by testing effectiveness in the following order: gain in specificity for fixed 98% sensitivity, decrease in NLR, gain in PLR, and gain in pAUC over 95% to 100% sensitivity where gain is the difference between the OA/US and IUS values.

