2.1.4. Sample Size Calculations

The sample size will be based on the primary effectiveness endpoint, namely the gain in specificity for fixed 98% sensitivity. This calculation depends upon the number of image sets (one per mass) to be read, the number of readers, as well as the inter-reader variability associated with the underlying models used for analysis.

The test of the primary hypothesis is powered to detect a 10% absolute specificity advantage (superiority) as the alternative hypothesis with no specificity advantage as the null hypothesis. The primary endpoint will be evaluated in the following testable hypotheses:

$$H_0: S_{\text{Imagio}} = S_{\text{IUS}}$$

$$H_1: S_{\text{Imagio}} \neq S_{\text{IUS}}$$

where S_{Imagio} and S_{IUS} represent specificity, values associated with Imagio (IUS + OA) and IUS.

The sample size calculations conservatively assume that both readers and masses are random effects; an ANOVA model will be used to compute sample size. The sample size was computed using the following statistical software written by Stephen Hillis and entitled: Multi-Reader Sample Size Program for Diagnostic Studies [<http://perception.radiology.uiowa.edu>].

For 80% power, a two-sided hypothesis test with a two-sided 5% alpha, and 15 readers, a sample size of 854 image sets is needed to detect a 10% absolute advantage in specificity for Imagio (IUS + OA) vs IUS, assuming a fixed 98% sensitivity and the same intra- and inter-reader standard deviation observed in the Reader-1 Feasibility Study.

The supporting calculations including the software output follow:

```
Results for Feasibility variance estimates

User-supplied parameter or pilot-study values:
  Design : factorial
  Tests : nonequivalence
  Readers and cases : both readers and cases random
  Input values : treat as known
  Alpha : 0.05
  Input Format : OR variance components with error covariances
test*reader var comp : 0.00203538
  Error variance : 0.03571
  Cov1 : 0.01106919
  Cov2 : 0.0061484
  Cov3 : 0.0043063
  c* : 120

User-supplied desired power, proposed readers & cases values
  Desired Power : 0.8
  Proposed max readers : 15
  Proposed max cases : 2000
  Proposed min readers : 15
  Proposed min cases : 20

Corresponding OR variance components, covariances, and correlations
test*reader var comp : 0.00203538
  Error variance : 0.03571
  Cov1 : 0.01106919
  Cov2 : 0.0061484
  Cov3 : 0.0043063
  r1 : 0.309974517
  r2 : 0.172175861
  r3 : 0.120590871

Sample Size Results

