2.1.11.2. Handling of Dropouts or Missing Data

Missing reader data will be reported (see protocol deviations). No imputation is planned for any excluded study data. The analysis methods can accommodate missing reader data.

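### SAP 2.1.3 excludes a case when the SenoGram does not display but re-presents it when an image does not: an unexplained, avoidable loss that only the test read can trigger

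*Combined protocol and SAP*

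**What the plan says.** SAP 2.1.3 (Analysis Populations) names two kinds of technical deviation, to be handled at a Protocol Deviation Meeting before the interim and final analyses. For images: "if an image display issue occurs, then that case will be re-presented to a reader once the technical issue is corrected". For the SenoGram: "If the SenoGram would not display to a reader, that case would be excluded from the analysis".

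The SenoGram belongs to the test condition. Under Protocol 5, Read 1 ends with a locked IUS rating that makes no use of it, and the Read 2 POM and BI-RADS category are assigned after viewing it. SAP 2.1.1 (item 10) and SAP 2.1.9 define the Imagio result in the same way.

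Three other provisions bear on the point:

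- Protocol 10.2 and SAP 2.1.4 say that "all complete reads will be included in all analyses" and call this an Intention-to-Diagnose approach, but they first carve out masses excluded for protocol deviations.
- SAP 2.1.11.2 says "No imputation is planned for any excluded study data", then adds that the analysis methods can cope with missing reader data.
- The sizing in SAP 2.1.4 assumes "Design : factorial".

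The documents do not say whether the excluded case is one reader's read or the mass for all 15 readers. They give no sensitivity analysis for these exclusions. The 60 overage masses in SAP 2.1.5 are for masses that prove unreadable, and SenoGram failure is not mentioned there.

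**The concern.** A SenoGram that does not display is a failure of something the test read needs and the control read does not. Removing the case makes the primary estimate a specificity gain among reads in which the SenoGram worked. That fits poorly with an Intention-to-Diagnose label, even though the carve-out for deviations permits it.

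The loss also looks unnecessary. Protocol 4 describes an output computed from scores and covariates the reader has already entered, and Protocol 8.1 puts a read monitor in every session. Showing the output again before the Read 2 form is locked appears no harder than showing the images again.

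Finally, the two readings of the excluded case give different datasets and very different losses. This matters because planned power at the cap is already just under 80%.

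**Working it through.** **Inputs.** From the sample-size output in SAP 2.1.4 (identical in Protocol 10.2): test-by-reader variance 0.00203538; error variance 0.03571; Cov1 0.01106919; Cov2 0.0061484; Cov3 0.0043063; pilot cases c* = 120; r = 15 readers; effect d = 0.10; two-sided alpha 0.05. The test is "powered to detect a 10% absolute specificity advantage (superiority) as the alternative hypothesis". The SenoGram failure rate f per read is not in the documents. It is assumed here to be 0.1% to 2%, independent across readers.

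**Formulas** (Obuchowski-Rockette, readers and cases random, c masses):

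- D = varTR + (c*/c)[varE − Cov1 + (r − 1)(Cov2 − Cov3)]
- noncentrality λ = r·d²/(2D)
- denominator df = D² / {[varTR + (c*/c)(varE − Cov1 − (Cov2 − Cov3))]²/(r − 1)}
- power from the noncentral F(1, df)

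**The plan's own figures first.** SAP 2.1.1 states: "For 80% power, a two-sided hypothesis test with a two-sided 5% alpha and 15 readers, a sample size of 854 image sets is needed" and "the 79% power with 840 image sets is deemed adequate to test the primary hypothesis test".

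At c = 840:

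- varE − Cov1 = 0.02464081, and 14 × (Cov2 − Cov3) = 14 × 0.0018421 = 0.0257894
- D = 0.00203538 + (120/840)(0.05043021) = 0.0092397
- λ = 15 × 0.01/(2 × 0.0092397) = 8.117
- df = 42.67, power = 0.795

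At c = 854, λ = 8.222 and power = 0.800 (the plan's output shows 0.801). The smallest c that reaches 0.80 is 854. Both stated figures reproduce, and no figure in the plan is wrong on this point.

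**Loss under each reading.** With 840 × 15 = 12,600 reads, the expected number of failed reads is 12,600·f. If the mass is dropped for everyone as soon as one reader is affected, the share of masses lost is 1 − (1 − f)^15. If only the affected read is dropped, power is approximated at 840(1 − f) masses.

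| f | reads failing | masses lost | masses left | power, whole mass dropped | power, read dropped |
|---|---|---|---|---|---|
| 0 | 0 | 0% | 840 | 0.795 | 0.795 |
| 0.1% | 13 | 1.5% | 827 | 0.791 | 0.795 |
| 0.5% | 63 | 7.2% | 779 | 0.772 | 0.794 |
| 1% | 126 | 14.0% | 722 | 0.747 | 0.792 |
| 2% | 252 | 26.1% | 620 | 0.695 | 0.789 |

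Dropping the whole mass keeps the reader-by-mass crossing but multiplies the loss. Dropping the read costs little power but leaves empty cells in the factorial.

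**Bias, for illustration only.** Suppose every failed read would have shown no gain. A 10-point gain among displayed reads is then 10(1 − f) over all reads: 9.9 points at 1% and 9.8 at 2%. A harsher assumption counts every failed benign read as positive in Read 2, with assumed specificities of 0.4 (control) and 0.5 (test). The gain is then 0.5(1 − f) − 0.4, or 9.5 points at 1% and 9.0 at 2%. Neither assumption comes from the documents.

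**The case against.** A reader might infer that the rule can only favour Imagio. The documents do not support that. Excluding a case removes its Read 1 and Read 2 together, so the estimated gain rises only if failed cases would have shown a smaller gain than the rest. SAP 2.1.3 describes the cause as a system error. If that is unrelated to the mass, little or no bias follows, and if it is related, the direction is unknown.

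A reader might also infer that the rule breaks the crossed design. That holds only if single reads are dropped. SAP 2.1.3 speaks of a case, and SAP 2.1.4 of masses excluded. On that reading, crossing and pairing are kept. For missing reads, SAP 2.1.11.2 says the methods can accommodate them, though it names no method.

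Nor does the plan remove test-condition failures across the board. OA images appear only in Read 2, and their display failures are re-presented. This also shows that the plan already accepts re-presentation for test-read material.

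Safeguards exist. Read monitors escalate problems they cannot resolve (Protocol 8.1), missing data are to be sought in real time (Protocol 10.2), and results-blinded parties review deviations, which are also reported by reader (Protocol 10.6). The SenoGram sentence could be meant for the residue that remediation cannot repair. If so, the SAP should say it, because the neighbouring image rule mentions correction and the SenoGram rule does not. Blinded review prevents selective decisions, but it does not alter a written rule tied to the test read.

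The failure rates are hypothetical. If failures cluster by mass, fewer masses are lost than the table shows.

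**Conclusion.** The point stands in limited form. SAP 2.1.3 excludes cases for a SenoGram display failure while re-presenting them for an image failure, and no reason is given. Only the test read can trigger the exclusion, so the estimate is conditional on the SenoGram displaying. No direction of bias can be claimed. Under the zero-gain illustration it is 0.1 to 0.2 points of a 10-point gain at 1% to 2% failure.

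The clearer cost is avoidable loss of data under a rule whose level is undefined. At 840 masses, power falls from 79.5% to between 79.1% and 69.5% if whole masses go, and to no lower than about 78.9% if only reads go. These ranges rest on assumed failure rates of 0.1% to 2%, independence across readers, and the Reader-01 variance components in the plan. The gap between the two readings is itself a reason to settle the level before the interim analysis.

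**What to change.** In SAP 2.1.3, replace the SenoGram exclusion with the rule already used for images: that reader completes the case once the SenoGram displays, before the Read 2 form is locked.

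For any case in which it still cannot be displayed:

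- state whether the read or the whole mass is excluded, and, if the read, which method handles the empty cell;
- report the number of such cases by reader and by diagnosis;
- add a sensitivity analysis that keeps these reads, for example with the Read 1 POM carried forward to represent no gain.

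The carry-forward should stay supportive. As a primary rule it would be a single imputation towards the null. It would also put Read 1 ratings into the Read 2 ROC curve for readers who had already seen the OA images.

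The cost is a few lines of SAP text, a few re-presented cases and one extra supportive analysis.

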2.1.4. Sample Size Calculations

The sample size will be based on the primary effectiveness endpoint, namely the gain in specificity for fixed 98% sensitivity. This calculation depends upon the number of image sets (one per mass) to be read, the number of readers, as well as the inter-reader variability associated with the underlying models used for analysis.

The test of the primary hypothesis is powered to detect a 10% absolute specificity advantage (superiority) as the alternative hypothesis with no specificity advantage as the null hypothesis. The primary endpoint will be evaluated in the following testable hypotheses:

$$H_0: S_{\text{Imagio}} = S_{\text{IUS}}$$

$$H_1: S_{\text{Imagio}} \neq S_{\text{IUS}}$$

where S_{Imagio} and S_{IUS} represent specificity, values associated with Imagio (IUS + OA) and IUS.

The sample size calculations conservatively assume that both readers and masses are random effects; an ANOVA model will be used to compute sample size. The sample size was computed using the following statistical software written by Stephen Hillis and entitled: Multi-Reader Sample Size Program for Diagnostic Studies [<http://perception.radiology.uiowa.edu>].

For 80% power, a two-sided hypothesis test with a two-sided 5% alpha, and 15 readers, a sample size of 854 image sets is needed to detect a 10% absolute advantage in specificity for Imagio (IUS + OA) vs IUS, assuming a fixed 98% sensitivity and the same intra- and inter-reader standard deviation observed in the Reader-1 Feasibility Study.

The supporting calculations including the software output follow:

```
Results for Feasibility variance estimates

User-supplied parameter or pilot-study values:
  Design : factorial
  Tests : nonequivalence
  Readers and cases : both readers and cases random
  Input values : treat as known
  Alpha : 0.05
  Input Format : OR variance components with error covariances
test*reader var comp : 0.00203538
  Error variance : 0.03571
  Cov1 : 0.01106919
  Cov2 : 0.0061484
  Cov3 : 0.0043063
  c* : 120

User-supplied desired power, proposed readers & cases values
  Desired Power : 0.8
  Proposed max readers : 15
  Proposed max cases : 2000
  Proposed min readers : 15
  Proposed min cases : 20

Corresponding OR variance components, covariances, and correlations
test*reader var comp : 0.00203538
  Error variance : 0.03571
  Cov1 : 0.01106919
  Cov2 : 0.0061484
  Cov3 : 0.0043063
  r1 : 0.309974517
  r2 : 0.172175861
  r3 : 0.120590871

Sample Size Results
effect size : readers : cases : power
  0.1 : 15 : 854 : 0.801
```

Initially, 360 masses will be read by all readers for the purposes of performing the interim analysis to assess the sources of variation and to rerun the sample size estimate for the primary effectiveness endpoint. Neither futility nor efficacy will be assessed; this is not an adaptive design.

The sample size may be increased from the minimum of 480 image sets to a maximum of 840 image sets (7 complete blocks) in increments of 120 masses per block. All masses used in the color balance algorithm will be excluded from the final analysis; these masses will be replaced from the PIONEER Pivotal overage masses and the PIONEER Pilot Study as needed.

The maximum sample size to be used for the study will be capped at 840 masses. An overage mass set will be set aside in case quality control issues are found with the images and replacement masses are needed. After excluding the pool of 840 masses and overage masses, approximately

900 masses will remain for independent SenoGram training. No masses used to train the SenoGram, will be in the pool of 840 study masses plus overage. We have removed the 29 masses from the pool of study masses which were mistakenly included from the original color balance algorithm.

Every effort will be made to identify missing reader generated data in real time. Each block of 120 masses will include 75 benign (72 benign + 3 high risk) and 45 malignant masses to represent the PIONEER study.

With the exception of masses excluded due to protocol deviations, all complete reads will be included in all analyses, consistent with an “Intention-to-Diagnose” approach.

2.1.5. Disposition of Masses

A total of 840 masses with 120 masses per block have been selected from the PIONEER Pivotal Study ITD population. The additional 60 overage masses allowed for replacement of any mass that might prove unreadable. Replacement of any masses will be documented in the Clinical Study Report (CSR).

2.1.6. Demographic and Other Baseline Characteristics

Clinical presentation and medical history (limited to the specific masses used from the PIONEER database), including the referral indication, palpability of mass, breast density, age, menopausal status, presence of breast implants, number of masses (in PIONEER), and mammographic intent will be summarized using descriptive statistics.

Summary tables will display demographic and baseline characteristics by diagnostic status (benign+TPB, cancer); TBP were the masses without biopsy which were declared to be Truth Panel Benign; high risk masses will be included with the benign masses.

2.1.7. Medical History and Concomitant Medications

Detailed medical history (as presented to the readers) will be listed. Concomitant medications are irrelevant to this study.

2.1.8. Effectiveness Methodology

The following approaches (Hillis OR-DBM MRMC 2.51) were used to treat readers as correlated and as random effects in analyses. [REDACTED]

[REDACTED]

[REDACTED]

Analysis 1 treats both as random, and thus results generalize to both the population of readers and cases – this is the situation for which the DBM and Obuchowski-Rockette (OR) procedures were originally designed. However, within the OR/DBM analysis framework one can also analyze the

data treating only cases as random (Analysis 2) or readers as random (Analysis 3), although we note that these analyses are not unique to OR/DBM. Analyses 2 and 3 are viewed as supportive analyses while Analysis 1 is viewed as the primary analysis approach.

For all three analyses, the null hypothesis of equal treatments is tested in part (a), diagnostic test difference 95% confidence intervals are given in part (b), and individual diagnostic test two-sided 95% confidence intervals are given in part (c) of the output. For the DBM procedure, parts (a) and (b) are based on the diagnostic test x reader x mass ANOVA of jackknife pseudo-values while part (c) is based on the reader x case ANOVA of jackknife pseudo-values for the specified diagnostic test. For the OR procedure, parts (a) and (b) are based on the diagnostic test x reader ANOVA of reader-performance outcomes (e.g., AUCs) while part (c) is based on the reader ANOVA of reader-performance outcomes for the specified diagnostic test. [REDACTED]

Different denominator “error terms” (these are the denominators used for the F statistics) are used as indicated for parts (a), (b), and (c) according to whether reader and case are treated as fixed or random factors, and their formulas are provided in the output. Note that the diagnostic test confidence intervals in part (c) are based only on the data for the specified diagnostic test, rather than the pooled data. Diagnostic test difference 95% confidence intervals for each reader are presented in part (d) of Analysis 2: for DBM each interval is based on the diagnostic test x mass ANOVA table for the specified reader; for OR each interval is based on the OR variance and Cov1 estimates computed separately for each reader.

Analysis 1

Our planned analysis (Analysis 1) treats both readers and masses as random samples. Results apply to the reader and mass populations — this is the situation for which DBM and OR were initially created.

Analysis 2

Analysis 2 treats only masses as a random sample. Results apply to the population of masses but only for the readers used in the study. For this analysis, inferences are based on the estimated error covariance matrix, treating readers as fixed. These two methods will give almost the same results for typical studies where the total number of cases is at least moderate (≥ 50). Diagnostic test differences and two-sided 95% confidence intervals are presented for each reader in part (d).

Analysis 3

Analysis 3 treats only readers as a random sample. Results apply to the population of readers but only for the masses used in this study. These results are based on a conventional diagnostic test x reader ANOVA for the AUCs (or other measures), where reader is a random factor and diagnostic test is a fixed factor which is included for completeness. This is the same as a repeated measures ANOVA where diagnostic test is the repeated measures factor, i.e., readers provide an outcome (e.g., AUC) for each diagnostic test. For two tests, this analysis is equivalent to a paired t test performed on the reader-specific AUC estimates. DBM and OR give the same results here, and it

does not matter with error covariance method is used with OR because the covariance does not enter into the F statistic.

See the respective equations for variance components and degrees of freedom (DF) in Appendix 1.

